4.2. Safety Analysis Set

The Safety analysis set (SAF) is defined as those subjects who received at least one dose of the investigational product according to actual treatment received.

5. GENERAL METHODOLOGY AND CONVENTIONS

Final analyses will occur after database lock after Last Subject Last Visit (LSLV).

5.1. Hypotheses and Decision Rules

This study was terminated. The termination decision was made for business reasons only and was not related to any safety or efficacy concerns regarding crisaborole. Only 40% of planned participants were enrolled at termination. Due to small sample size, no hypotheses testing and decision rules. No statistical analysis and comparison will be performed. Only descriptive summary will be generated for safety data and some efficacy endpoints.

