9. DATA ANALYSIS/STATISTICAL METHODS

Detailed methodology for summary and statistical analyses of the data collected in this study is outlined here and further detailed in a statistical analysis plan (SAP), which will be maintained by the sponsor. The SAP may modify what is outlined in the protocol where appropriate; however, any major modifications of the primary endpoint definitions or their analyses will also be reflected in a protocol amendment.

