9.2.2. Analysis of the Primary Endpoint

The primary endpoint, EASI % change from baseline, will be analyzed using a mixed-effect repeated measures model that includes the fixed effects of treatment, visit as class variable,

treatment by visit interaction. Within-subject variability will be accounted for using a random effect with the first order autoregressive (AR(1)) covariance matrix. For the comparison of crisaborole versus vehicle, the model will also include factor of Cohort.

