1. VERSION HISTORY

This SAP for Study C3291037 is based on the protocol amendment 3 dated 12AUG2019.

Table 1. Summary of Major Changes in SAP Amendments

Version/Date	Associated Protocol Amendment	Specific Changes	Rationale
1 16MAY2018	Original 16MAR2018	Not Applicable	Not Applicable
2 27SEP2019	Protocol Amendment 3 12 Aug 2019	Removal of telephone follow-up at Day 36; addition of a clinic visit at Day 43; addition of restrictions to concurrent medications during the follow-up phase; and changes to the pruritis scale descriptions, endpoints, and analysis.	Per Protocol Amendment 3
3 10NOV2020	Protocol Amendment 3 12 Aug 2019	Modifications of efficacy and patient reported outcomes endpoints: 
 • Only descriptive summary will be provided for primary efficacy and selected secondary endpoints. • No summary/analysis will be done for tertiary/exploratory endpoints. Appendix 8 Listing of Abbreviations was added	Study termination

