2. INTRODUCTION

This SAP provides the detailed methodology for summary and statistical analyses of the data collected in Study C3291037. This document may modify the plans outlined in the protocol; however, any major modifications of the primary endpoint definition or its analysis will also be reflected in a protocol amendment.

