2.1. Study Objectives

Study objectives and corresponding endpoints are provided in the [Table 2](#) below.

Table 2. Study Objectives and Endpoints

Primary Efficacy Objective	Primary Efficacy Endpoint

 To compare the efficacy of crisaborole ointment, 2% applied twice daily (BID) versus vehicle in pediatric and adult subjects (ages 2 years and older) with mild to moderate Atopic Dermatitis (AD). 	
 Percent change from baseline in the Eczema Area and Severity Index (EASI) total score at Day 29.
Primary Safety Objectives	Primary Safety Endpoints

 To evaluate the safety and local tolerability of crisaborole ointment, 2% applied BID versus vehicle in pediatric and adult subjects (ages 2 years and older) with mild to moderate AD. To evaluate the safety and local tolerability of hydrocortisone butyrate cream 0.1% and pimecrolimus cream 1% applied BID in pediatric and adult subjects (ages 2 years and older) with mild to moderate AD. 	
 Adverse Events (AEs), Serious Adverse Events (SAEs), local tolerability, discontinuations and clinically significant changes in vital signs and clinical laboratory parameters.
Secondary Objectives	Secondary Endpoints

 To evaluate the effect of crisaborole ointment, 2% applied BID versus vehicle on additional efficacy endpoints over time in pediatric and adult subjects (ages 2 years and older) with mild to moderate AD. To evaluate the efficacy of crisaborole ointment, 2% BID versus hydrocortisone butyrate cream 0.1% and pimecrolimus cream 1% applied BID in pediatric and adult subjects (ages 2 years and older) with mild to moderate AD. 	
Efficacy endpoints:
 
 Percent change from baseline in EASI total score by scheduled time points except Day 29. Achievement of success in the Investigator's Static Global Assessment (ISGA) (defined as an ISGA score of Clear (0) or Almost Clear (1) with at least a 2-grade improvement from baseline) by scheduled time points. Achievement of ISGA score of clear (0) or almost clear (1) by scheduled time points. Achievement of EASI75 ($\geq 75\%$ improvement from baseline) by scheduled time points. Time to EASI75. Change from baseline in %BSA by scheduled time points.

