2.2. Study Design

This is a Phase 3b/4, multicenter, randomized, assessor blinded, vehicle and active (topical corticosteroid [TCS] and topical calcineurin inhibitor [TCI]) controlled study of the efficacy, safety and local tolerability of crisaborole ointment, 2% in pediatric and adult subjects, ages 2 years and older, with mild to moderate AD involving at least 5% treatable body surface area (%BSA). Treatment will be clinical assessor blinded for all treatment arms and double blinded for crisaborole ointment, 2% and vehicle treatment arms.

A total of approximately 600 subjects will be enrolled in the study, of which at least 150 subjects aged 2-6; at least 140 subjects aged 7-11; at least 120 subjects aged 12-17, and up to 90 subjects will be adults. Following the screening period (up to 35 days prior to Baseline/Day 1), eligible subjects will be randomized at the Baseline/Day 1 visit.

Randomization will be stratified by eligibility for TCS or TCI treatment as per national approved labels and eligibility provided in Section 4 of the protocol. Cohort 1 will be for subjects who are eligible for TCS therapy, and Cohort 2 will be for subjects who are not eligible for TCS therapy but eligible for TCI therapy. The investigational product will be applied BID for 28 days to the Treatable BSA identified at Baseline/Day 1. Any new AD on treatment eligible locations occurring following Baseline/Day 1 should also be treated with the study drug after consultation with the Investigator at the next visit.

The primary efficacy endpoint is the percent change from baseline in the EASI total score at Day 29.

For the efficacy comparison of crisaborole versus vehicle, subjects from both Cohort 1 and Cohort 2 are included in the analysis, adjusted for cohort effect. For the efficacy comparison of crisaborole versus TCS, only subjects from Cohort 1 are included in the analysis. For the comparison of crisaborole versus TCI, only subjects from Cohort 2 are included in the analysis.

[figure not shown]
Safety and efficacy assessments will be conducted at the investigator site by a clinical assessor blinded for treatment arms.

A sub-study will be conducted at selected investigator sites to evaluate differences of changes in epidermal skin thickness as measured by Optical Coherence Tomography (OCT) between treatment groups in Cohort 1. Detailed statistical analysis for sub-study will be given in a separate SAP.

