6. ANALYSES AND SUMMARIES

Due to study termination, only 40% of participants were enrolled. No statistical analysis and comparison will be performed. Only descriptive summary will be performed for selected efficacy and PRO endpoints.

Summary of selected efficacy and PRO endpoints will be based on FAS population. [Section 5.2](#) provides treatment groups for summary.

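### After early termination the SAP drops the crisaborole-vehicle estimate along with the test; the small sample justifies only the second, and the change is not recorded in a protocol amendment

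*SAP*

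**What the plan says.** Protocol 9.2.2 analyses percent change in EASI with a mixed-effect repeated-measures model (treatment, visit, treatment by visit, AR(1) covariance) and adds: "For the comparison of crisaborole versus vehicle, the model will also include factor of Cohort".

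SAP version 3, written after termination, withdraws this. Section 5.1 says "Due to small sample size, no hypotheses testing and decision rules. No statistical analysis and comparison will be performed", and section 6 repeats it: "No statistical analysis and comparison will be performed. Only descriptive summary will be performed for selected efficacy and PRO endpoints". Section 6.1.1 leaves descriptive statistics and a graph of observed percent change, and section 5.3.2 uses observed data only for continuous endpoints. The change is logged in SAP Table 1, with study termination as the reason: "Only descriptive summary will be provided for primary efficacy and selected secondary endpoints". The protocol version cited there is Amendment 3 of 12 August 2019; SAP version 3 is dated 10 November 2020.

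The front of the SAP keeps the design as planned. The primary objective in Table 2 is still "To compare the efficacy of crisaborole ointment, 2% applied twice daily (BID) versus vehicle", and section 2.2 still says that "subjects from both Cohort 1 and Cohort 2 are included in the analysis, adjusted for cohort effect".

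Both documents carry a rule for such changes. Protocol section 9 lets the SAP modify the protocol where appropriate, but "any major modifications of the primary endpoint definitions or their analyses will also be reflected in a protocol amendment". SAP section 2 repeats that "any major modifications of the primary endpoint definition or its analysis will also be reflected in a protocol amendment".

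**The concern.** Section 5.1 gives one reason, small sample size, for two separate decisions: no hypothesis test, and no between-arm comparison of any kind. A small sample weakens a test. It does not make an effect estimate invalid; it makes the interval wider, and the interval shows that. The stop was for business reasons unrelated to safety or efficacy, and neither document plans an interim analysis (Protocol 9.4, SAP 7.2), so no stopping rule complicates estimation.

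Two things are at stake. First, the trial would report its primary endpoint without stating the quantity that its primary objective names, and readers would have to build it themselves from observed cases. Second, the protocol supplied and the SAP prescribe different primary analyses, and the amendment that both documents promise for a major change is not cited.

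**Working it through.** **Inputs.** SD 34, target difference 12 points, two-sided 0.05, 150 per arm versus vehicle, 75 versus 150 for each active comparator (Protocol 9.1); allocation 1:1:2 in each cohort (Protocol 4.3); 40% of about 600 enrolled (SAP 5.1).

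**Reproducing the plan.** Half-width = 1.96 × SD × √(1/a + 1/b); power = Φ(12/SE − 1.96).
- 150 versus 150: SE = 34 × √(2/150) = 3.93; power = Φ(3.06 − 1.96) = 86.4% (stated: 86%); half-width 7.7.
- 75 versus 150: 1.96 × 34 × √(1/75 + 1/150) = 9.4 (stated: 9.4).

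**At termination.** Assumption: enrolment fell evenly, so 0.40 × 600 = 240 subjects, with 60 on crisaborole and 60 on vehicle. The documents give no counts by arm or cohort.

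| SD | Half-width, 60 vs 60 | Power for 12 points |
|---|---|---|
| 30 | 10.7 | 59% |
| 34 | 12.2 | 49% |
| 40 | 14.3 | 38% |

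At SD 34 the half-width is 12.2/9.4 = 1.3 times the figure that Protocol 9.1 treats as sufficient for putting crisaborole in context against the active comparators. For each active comparator, with equal cohorts (30 versus 60), it is 1.96 × 34 × √(1/30 + 1/60) = 14.9.

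**What a reader can rebuild.** SAP 5.2 gives N, mean, SD and standard error for crisaborole and vehicle with cohorts combined, so a crude difference and CI follow directly. SAP 6.4 adds summaries by cohort. Crisaborole and vehicle are allocated 1:1 within each cohort, so cohort adjustment should move the difference little.

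**What observed-case summaries can lose.** The planned model uses Days 8, 15 and 22 for subjects who lack Day 29; observed-case summaries do not. The documents give no dropout rate, so this was simulated under stated assumptions:
- true difference 12.1 (38.9 versus 26.8, Protocol 9.1), SD 34;
- assumed Day 22 means of −34 and −23, AR(1) correlation 0.5 to 0.85;
- 5% to 20% of Day 29 values missing, more often after a poor Day 22 response (logistic).

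| Slope per point of Day 22 change | Odds ratio per SD | Shrinkage of the observed-case difference |
|---|---|---|
| 0.01 | exp(0.34) = 1.4 | 0.2 points or less |
| 0.02 | exp(0.68) = 2.0 | about 0.1 to 0.7 points |
| 0.05 | exp(1.7) = 5.5 | about 0.5 to 1.9 points |

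A likelihood estimate that uses Day 22 stays at about 12.1, but that follows from how the missingness was set up. If it depends on the unseen Day 29 value itself (slope 0.05), the likelihood estimate also falls, to about 10.0 to 11.7. In runs with 60 per arm, the model's half-width was within about 0.2 points of the observed-case one, so it brings no material gain in precision.

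**The case against.** The sponsor can fairly say that the sample size was built on a test, that the test lost its power, and that descriptive reporting was a reasoned and logged response. No passage requires an effect estimate after termination. The only between-arm interval in the plan is the one against the active comparators in Protocol 9.1; none is promised against vehicle. The crude difference is one line of arithmetic from the SAP 5.2 output, and even 1.9 points is small beside 12.2. A 95% CI also tends to be read as a test: at the design effect it would run from about −0.2 to 24.2.

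Most of this stands. It limits the size of the point and makes the interval a recommendation rather than a broken promise. It does not turn small sample size into a reason against estimation, and SAP 5.2.4 itself keeps 95% intervals for Kaplan-Meier medians and quartiles. It does not answer the amendment rule either: removing the primary model and its contrast is hard to call anything but a major modification of the primary analysis.

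A reader might infer a concealed switch of the primary analysis. The documents do not support that: Table 1 states the change and its reason, and the endpoint definition is unchanged. A reader might also infer that SAP 2.2 and 5.1 give rival instructions. Section 2.2 still says that about 600 subjects will be enrolled, so it is as-designed text; sections 5.1 and 6 are explicit, and a programmer would follow them.

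**Conclusion.** The point holds at modest size and should be fixed. SAP version 3 replaces the Protocol 9.2.2 analysis with arm summaries, so no planned output states the crisaborole-vehicle difference. Power of about 49% justifies dropping the test; a half-width of about 12.2 points (10.7 to 14.3) does not justify dropping the estimate. That last step is a statistical judgement, whereas the uncited amendment and the mismatch between protocol and SAP can be read directly from the documents.

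It would go too far to say that observed-case reporting seriously distorts the result. The bias depends on missingness that the documents do not describe: about 0 to 0.7 points under weak to moderate dependence on Day 22 response, and up to about 1.9 only under strong dependence. The model removes it only if missingness depends on visits that were observed. The precision figures assume even enrolment at 40% and an SD near 34.

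**What to change.** Keep the exclusion of hypothesis tests and decision rules. In SAP 5.1 and 6, replace the sentence that rules out all statistical analysis and comparison with wording such as:

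*The crisaborole minus vehicle difference in EASI percent change from baseline at Day 29 and its 95% CI will be reported from the Protocol 9.2.2 repeated-measures model with the cohort factor, for estimation only, with no p-value and no claim of success.*

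The contrasts with TCS (Cohort 1) and TCI (Cohort 2) are optional, given half-widths of about 14.9 points.

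Before unblinding, settle whether baseline EASI is in the model. The Protocol Summary includes it, section 9.2.2 omits it, and section 9.2.3 calls it an additional covariate for change-from-baseline endpoints.

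Record the change to the primary analysis in a protocol amendment, as both documents say, and mark SAP 2.1 and 2.2 as as-designed text. If the sponsor keeps descriptive reporting only, that record and that marking are the minimum.

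The cost is SAP wording and one model-based contrast on data already collected, plus an amendment that needs IRB/EC approval (Protocol 12.1). The downside is that a wide interval can be over-read, so the estimation-only label should accompany it wherever it is reported.

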5.2. General Methods

In general, number and percent will be presented for binary and categorical variables. Number, mean, standard deviation, standard error of the mean, median, minimum, and maximum will be presented for continuous variables. In addition, graphics may be used to present the data – specific details will be outlined in the study List of Table (LOT).

Descriptive statistics will be provided for:

- Crisaborole ointment, 2% applied BID (Cohort 1);
- Crisaborole ointment, 2% applied BID (Cohort 2);
- Crisaborole ointment, 2% applied BID (combined Cohorts 1 and 2);
- Vehicle (combined Cohorts 1 and 2);
- Hydrocortisone butyrate cream, 0.1% BID (TCS, Cohort 1);
- Pimecrolimus cream, 1% BID (TCI, Cohort 2);
- Total – only for disposition, evaluation, demographic and baseline characteristics.

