4.1. Inclusion Criteria

4.1.1. Inclusion Criteria – All Cohorts

Subjects must meet all of the following inclusion criteria to be eligible for enrollment into the study:

1. Is male or female 2 years and older at the Screening visit/time of informed consent/assent.
2. Has a clinical diagnosis of AD according to the criteria of Hanifin and Rajka (See [Appendix 2](#)).
3. Has AD involvement of $\geq 5\%$ Treatable %BSA (excluding the scalp) at Baseline/Day 1.
4. Has an ISGA score of Mild (2) or Moderate (3) (excluding the scalp) at Baseline/Day 1.
5. Female subjects of childbearing potential who have a negative urine pregnancy test at the screening visit and negative urine pregnancy test at the baseline visit prior to randomization. A female is of childbearing potential if, in the opinion of the investigator, she is biologically capable of having children (includes any female who has experienced menarche and does not meet the criteria for females not of childbearing potential).
6. Female subjects of non-childbearing potential must meet at least 1 of the following criteria:
 - a. Achieved postmenopausal status, defined as follows: cessation of regular menses for at least 12 consecutive months with no alternative pathological or physiological cause; have a serum follicle-stimulating hormone (FSH) level confirming the postmenopausal state;
 - b. Have undergone a documented hysterectomy and/or bilateral oophorectomy;
 - c. Have medically confirmed ovarian failure.

All other female subjects (including female subjects with tubal ligations) are considered to be of childbearing potential.

7. Evidence of a personally signed and dated informed consent/assent document indicating that the subject [or parent(s)/legal guardian] has been informed of all pertinent aspects of the study.
8. Willing and able to comply with scheduled visits, treatment plan, laboratory tests and other study procedures.

4.1.2. Inclusion Criteria – Cohort 1

1. Subjects considered to be a candidate for hydrocortisone butyrate cream, 0.1% therapy according to the national approved labeling.

4.1.3. Inclusion Criteria – Cohort 2

1. Subjects who are not considered candidates for treatment with a topical corticosteroid because it is either inadvisable or not appropriate according to the national approved labeling. This may include:
 - Intolerance to topical corticosteroids;
 - Lack of effect of topical corticosteroids;

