6.4. Subset Analyses

Summary of percentage change from baseline in EASI will be summarized by treatment and by cohort, age group, sex, race, baseline ISGA, and geographic region.

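### Outside EASI percent change from baseline, the efficacy and PRO summaries show vehicle only pooled over cohorts, so TCS, TCI and cohort-level crisaborole have no own-cohort vehicle column

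*SAP*

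**What the plan says.** SAP 5.2 (General Methods) lists the groups for descriptive statistics. Crisaborole has three entries: "Crisaborole ointment, 2% applied BID (Cohort 1", "Crisaborole ointment, 2% applied BID (Cohort 2" and "Crisaborole ointment, 2% applied BID (combined Cohorts 1 and 2" (closing brackets dropped here and below). The steroid has one, "Hydrocortisone butyrate cream, 0.1% BID (TCS, Cohort 1", and pimecrolimus has one, for Cohort 2. Vehicle has one: "Vehicle (combined Cohorts 1 and 2".

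SAP 6 makes this list govern the selected efficacy and PRO summaries, saying that Section 5.2 "provides treatment groups for summary". SAP 6.1 and 6.2 then go through the endpoints without adding any group. The one by-cohort display is in SAP 6.4: "Summary of percentage change from baseline in EASI will be summarized by treatment and by cohort", followed by other subgroup factors.

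Protocol 4.3 assigns subjects to a cohort first and then randomises 1:1:2 to crisaborole, vehicle and that cohort's active comparator. Protocol 4.1.3 defines Cohort 2 as "Subjects who are not considered candidates for treatment with a topical corticosteroid because it is either inadvisable or not appropriate", and its examples include intolerance and lack of effect of topical steroids. SAP 5.1 records termination at 40% of planned enrolment and limits the output to descriptive summaries.

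**The concern.** The randomised control for TCS and for Cohort 1 crisaborole is Cohort 1 vehicle. For TCI and Cohort 2 crisaborole it is Cohort 2 vehicle. Pooled vehicle is neither: it mixes a steroid-eligible population with one selected for not being steroid candidates, in proportions the SAP does not state.

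The protocol treated cohort as something to control. The crisaborole–vehicle comparison was to include a cohort factor in the repeated measures model (Protocol 9.2.2) and to stratify the CMH and log-rank tests by cohort (9.2.3). SAP 5.1 drops those analyses, which leaves the table columns as the only means of keeping like with like. The trial's stated purpose is to put crisaborole in context against TCS and TCI. A reader will want to know whether each active comparator did better than vehicle in its own population, and whether crisaborole's margin over vehicle differs between cohorts. For most endpoints the planned columns cannot show either.

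**Working it through.** **The planning figures.** Protocol 9.1 assumes 150 per arm, a 12-point difference and SD 34, with two-sided alpha 0.05. These give power 0.864 (normal) or 0.861 (noncentral t), against the stated 86%. The half-width 1.96 × 34 × √(1/75 + 1/150) = 9.42 agrees with the stated 9.4. Neither figure is in dispute. The SD is used below only for precision.

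**Which endpoints lack own-cohort vehicle.** Setting the SAP 5.2 list against SAP 6.1, 6.2 and 6.4:

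| Summary | Vehicle by cohort? |
|---|---|
| EASI percent change from baseline (6.1.1) | Yes, through 6.4 |
| EASI percent change, Day 29 to Day 43 (6.1.2) | No |
| ISGA success, ISGA 0/1, EASI75 (6.1.3–6.1.5) | No |
| Time to EASI75, %BSA (6.1.6–6.1.7) | No |
| Peak Pruritus NRS change, ≥2-point and ≥3-point improvement (6.2.1, 6.2.4, 6.2.5) | No |
| DLQI, CDLQI, DFI (6.2.6–6.2.8) | No |

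**Size of the misreading.** Let m1 and m2 be the vehicle means (or response proportions) in the two cohorts, w1 and w2 = 1 − w1 the cohort shares of vehicle subjects, and d = m1 − m2. Pooled vehicle is w1·m1 + w2·m2.

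- A Cohort 1 column minus pooled vehicle is off by m1 − (w1·m1 + w2·m2) = w2·d.
- A Cohort 2 column minus pooled vehicle is off by m2 − (w1·m1 + w2·m2) = −w1·d.
- If a reader compares crisaborole's apparent margin over vehicle between cohorts, the two errors add: w2·d + w1·d = d, whatever the split. The same holds for TCS's margin against TCI's.

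The documents give no cohort-specific vehicle response and no achieved split. Taking d = 5, 10 or 15 points as an assumed range, the absolute errors are:

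| Cohort 1 share (assumed) | Cohort 1 columns (TCS, crisaborole) | Cohort 2 columns (TCI, crisaborole) |
|---|---|---|
| 30% | 3.5, 7.0, 10.5 | 1.5, 3.0, 4.5 |
| 50% | 2.5, 5.0, 7.5 | 2.5, 5.0, 7.5 |
| 70% | 1.5, 3.0, 4.5 | 3.5, 7.0, 10.5 |

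The errors in the two cohorts run in opposite directions. The formula applies to means and proportions. It does not carry over to Kaplan-Meier medians, although the pooled curve mixes the cohorts in the same way.

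**What is not affected.** Crisaborole and vehicle are allocated 1:1 in both cohorts, so the two pooled columns have the same expected cohort mix and the cohort effect cancels apart from chance imbalance. Cohort 1 crisaborole sits beside TCS and Cohort 2 crisaborole beside TCI, so those contrasts are matched too.

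**Cell sizes after the change.** 40% of 600 is 240. With equal cohorts (assumed), each has 120, and one quarter of that is 30 vehicle subjects. With Cohort 1 at 30% to 70% of enrolment, the two vehicle cells range from 18 to 42. For ISGA success, using the pooled Phase 3 vehicle rate of 21.8% from Protocol 9.1 purely for precision, the standard error is √(0.218 × 0.782/30) = 7.5 percentage points for 30 subjects, against √(0.218 × 0.782/60) = 5.3 for the pooled 60.

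**The case against.** The case for leaving the list alone is substantial.

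*The columns match the declared contrasts.* The protocol and SAP name three comparisons: crisaborole with vehicle over both cohorts, crisaborole with TCS in Cohort 1, and crisaborole with TCI in Cohort 2. SAP 5.2 serves all three. No efficacy objective sets TCS or TCI against vehicle, and SAP 5.1 rules out formal comparisons. This stands, and it means that no planned estimate or test is wrong.

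*A reader might infer that every visible contrast with vehicle is confounded by cohort.* It is not: pooled crisaborole against pooled vehicle, the trial's primary comparison, is protected by the equal allocation.

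*A reader might infer that no within-cohort check of the active comparators is possible.* SAP 6.4 provides one for EASI percent change from baseline, which includes the primary endpoint. The gap concerns the remaining endpoints.

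*It is tempting to express the error as a share of the planned 12-point effect.* That effect is on EASI percent reduction at Day 29, which SAP 6.4 already covers by cohort. The documents offer no comparable yardstick for the affected endpoints.

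*Splitting vehicle trades bias for noise.* With equal cohorts and SD 34, TCS (60) minus Cohort 1 vehicle (30) has standard error 34 × √(1/60 + 1/30) = 7.6, against 34 × √(1/60 + 1/60) = 6.2 for pooled vehicle. The pooled reading has the smaller mean squared error unless (d/2)² exceeds 57.8 − 38.5 = 19.3, that is, unless d exceeds about 8.8 points. The arithmetic is right on the EASI scale, but it argues against replacing the pooled column, and nothing need be replaced.

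*Some cells will be very small.* Peak Pruritus NRS is summarised only from age 12 and DLQI only from age 16. Taking the planned 120 adolescents (a minimum) and 90 adults (a maximum) out of 600 gives 35%, so about 10 of 30 vehicle subjects per cohort for itch, and fewer for DLQI. This also stands, but the cohort-level crisaborole columns are already planned at the same size.

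Finally, the List of Tables is not among the documents and might add these columns. SAP 5.2 refers to it only for details of graphics.

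**Conclusion.** The concern holds as a gap in presentation. For every efficacy and PRO summary except EASI percent change from baseline, TCS, TCI and cohort-level crisaborole are shown without their own randomised vehicle group. Reading them against the vehicle column provided is off by the other cohort's vehicle share times d. The whole of d enters when margins over vehicle are compared between cohorts. Whether that is negligible or material depends on d and the split, and the values tabulated above are illustrations, not estimates.

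The consequence is a misleading descriptive reading. It does not touch the primary comparison, the crisaborole–TCS and crisaborole–TCI contrasts, or any inference, since none is planned. The change is worth making because it is specific and nearly free, and because it presents results by the groups within which the trial randomised.

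**What to change.** Add two entries to the SAP 5.2 list, *Vehicle (Cohort 1)* and *Vehicle (Cohort 2)*, for all efficacy and PRO tables and figures, and keep the pooled crisaborole and vehicle entries. A layout that follows the randomisation is Cohort 1 (crisaborole, vehicle, TCS), Cohort 2 (crisaborole, vehicle, TCI), then combined crisaborole and vehicle. Show the number of subjects in each column so that readers can see the cohort mix behind pooled vehicle.

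The cost is two columns per table and two lines per figure, with no new data and no change to any endpoint or analysis set. The drawback is imprecise cells, especially for the age-restricted PROs; a table note should warn against over-reading them.
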